### 6.12.7. Immunogenicity

Blood samples for immunogenicity testing will be collected to determine antibody production against insulin lispro for all enrolled patients since Visit 2 prior to the first dose of study-provided prandial insulin treatment. Therefore, the blood sample result at Visit 2 will be considered as the anti-insulin lispro level at baseline for this study.

Patients who complete the 4-week safety follow-up visit (Visit 801) and have treatment-emergent anti-insulin lispro antibodies that have not returned to prespecified baseline range (Visit 2) will be asked to participate in follow-up to monitor antibody levels. The assessment of immunogenicity will include analyses of treatment-emergent anti-insulin lispro antibody up to Visit 801.

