eCRF Visit Number	1	2	3a	4a	5	6a	7	8	9a	10	11	12a	13	14a	15	16	17	18	801	ED ^b
Visit Window (± days)		3	3	3	3	3	3	4	3	3	7	7	7	7	7	7	7	7	7	
Time on Study Relative to First Active Treatment Dose (weeks)	-9	-8	-7	-6	-4	-2	-1	0	1	2	4	6	8	10	12	18	22	26	30	
Laboratory Assessments																				
Patient fasts prior to visit		X						X											X	X
MMTT ^f								X											X	
Urinalysis panel	X																			
Pregnancy test ^s	X							X												
Follicle-stimulating hormone test ^t	X																			
Chemistry	X							X											X	X
Fasting serum glucose		X																		
Hematology	X							X											X	X
1,5-Anhydroglucitol								X			X				X				X	X
Hemoglobin A1c	X						X	X			X		X		X				X	X
Lipid profile								X											X	X
Anti-insulin lispro antibodies		X						X		X	X				X				X	X
Health outcomes questionnaires^u																				
ITSQ		X						X											X	X
EQ-5D-5L		X						X											X	X
WPAI-GH		X						X											X	X

Abbreviations: AE = adverse event; BP = blood pressure; ECG = electrocardiogram; eCRF = electronic case report form; ED = early discontinuation; EQ-5D-5L = European Quality of Life – 5 Dimensions 5 Level; FBG = fasting blood glucose; hypo = hypoglycemia; IP = investigational product; ITSQ = Insulin Treatment Satisfaction Questionnaire; IWRS = interactive web response system; MMTT = mixed-meal tolerance test; SMBG = self-monitored blood glucose; WPAI-GH = Work Productivity and Activity Impairment Questionnaire General Health.

- a Telephone visits are indicated by shaded columns. Activities include:
 - Record visit in IWRS.
 - Collect AEs and concomitant medications.
 - Review blood glucose readings and study drug doses. Recommendations for basal or prandial insulin adjustments are provided, if necessary by the investigator or designee.
 - Review hypoglycemic events.
 - Provide reminders regarding scheduled visits, fasting, and SMBG profiles, as applicable.
- b Patients who have been randomized will be asked to return for the ED visit in a fasting state unless patient is already fasting and at the site when the decision to discontinue is made. Patients who discontinue during the lead-in period prior to randomization, and who are not already at the site, will be asked to return for the ED in a nonfasting state and all activities should be completed except for laboratory tests and completing the questionnaires (ITSQ, EQ-5D-5L, and WPAI-GH).

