- c Randomization should occur after all Visit 8 procedures including MMTT. If MMTT is rescheduled post Visit 8, randomization should not occur until baseline MMTT is completed. The patient will administer their first dose of study insulin with the first meal after the MMTT has been completed and randomization has occurred.
- d Physical examination shall be performed at Visit 1. It shall be performed at other visits if deemed necessary by the investigator.
- e Patients should be advised to remove their shoes and empty their pockets before the body weight is obtained.
- f Vital sign measurements must be taken before obtaining an ECG tracing and before collection of blood samples for laboratory testing. These measurements should be determined after patients have been seated quietly for at least 5 minutes in a chair with feet on the floor. The arm used for BP measurement should be supported at heart level
- g Initial training at Visit 2 will include diabetes education and nutrition counseling. Appropriate site personnel will administer training and education using locally approved diabetes education/training materials and programs or by using other materials that may be provided by the Sponsor. Patients may be provided abbreviated training and education at visits following Visit 2 based upon patient needs.
- h Only applies to patients treated with insulin glulisine, insulin aspart, regular human insulin, or premixed insulin.
- i Patients will be transferred to insulin glargine U-100 once daily or to degludec U-100 once daily at Visit 2 if the patient enters the study on any other basal insulin regimen. Investigators will determine the appropriate basal insulin regimen for each patient. Basal insulin should be titrated during the 8-week lead-in period to the target FBG. Basal insulin dose may be adjusted if needed to facilitate optimal prandial insulin dosing during the intensive titration period (Weeks 0 to 12) or for safety reasons. Thereafter, during the maintenance period (Weeks 12 to 26), it is expected that adjustments to basal insulin doses would be for safety reasons such as hypoglycemia or unacceptable hyperglycemia.
- j Assessments of the basal insulin dose should be made at minimum weekly during the lead-in period, including Weeks -5 and -3. Assessment of the prandial insulin dose should be made at minimum weekly during the initial 12 weeks after randomization, including Weeks 3, 5, 7, 9, and 11. See also Sections [7.2.1.3](#) and [7.2.1.4](#).

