Patients treated with insulin aspart, insulin glulisine, regular human insulin, or premixed insulin will be transferred to insulin lispro at Visit 2, so that all patients will be treated with insulin lispro throughout the lead-in period. Patients treated with 1 to 2 prandial injections a day or premixed insulin prior to study entry will transition to 3 injections a day of prandial insulin lispro at the beginning of the lead-in period. At Visit 8, patients will be randomized to either LY900014 or insulin lispro at each meal. During the initial 12 weeks after randomization (intensive titration period), prandial insulin doses should be titrated as necessary in order to meet the target self-monitored blood glucose (SMBG) levels. Basal insulin may be titrated as needed to facilitate optimal prandial dosing or for safety reasons such as hypoglycemia or unacceptable hyperglycemia. Thereafter, during the maintenance period (Weeks 12-26 of treatment), it is expected that adjustments to prandial and basal insulin doses would be to maintain glycemic control or for safety reasons such as hypoglycemia or unacceptable hyperglycemia.

[Figure ITSE.1](#) illustrates the study design.

Abbreviations: T = telephone visit; wk = week.

- a At Visit 2, patients treated with insulin aspart, insulin glulisine, regular insulin, or premixed insulin will be transferred to insulin lispro. At Visit 2, patients treated with a basal insulin regimen other than insulin glargine U-100 or insulin degludec will be transferred to insulin glargine U-100 once daily or insulin degludec U-100 once daily. At Visit 8, patients will be randomized to either insulin lispro or LY900014 and continue their basal insulin regimen.
- b Titrate basal insulin.
- c Titrate prandial insulin (insulin lispro or LY900014).
- d Patients will discontinue study insulins at Week 26.

Figure ITSE.1. Illustration of study design for Clinical Protocol 18B-FH-ITSE.

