**Objectives and Endpoints**

Objectives	Endpoints
Other Secondary Objectives (Continued)	

 
To compare LY900014 and insulin lispro with respect to the proportion of patients achieving HbA1c targets
 
	
 
The proportion of patients with HbA1c <7% and ≤6.5% at Week 26
 

Tertiary/Exploratory Objectives	

 
To compare the safety of LY900014 relative to insulin lispro
 
	
 
Adverse events, vital signs, chemistry, and hematology laboratory measures
 

 
To compare the incidence of treatment-emergent anti-insulin lispro antibodies for LY900014 and insulin lispro
 
	
 
Incidence of treatment-emergent positive anti-insulin lispro antibodies
 

 
To compare LY900014 and insulin lispro with respect to quality of life as measured by the EQ-5D-5L
 
	
 
Change from baseline in EQ-5D-5L UK-population based health state index score and EQ-VAS score at Week 26
 

 
To compare LY900014 and insulin lispro with respect to diabetes treatment satisfaction as measured by the ITSQ
 
	
 
Change from baseline in ITSQ regimen inconvenience and lifestyle flexibility domain scores at Week 26
 

 
To compare LY900014 and insulin lispro with respect to the impact that diabetes has on the ability to work and perform regular activities as measured by the WPAI-GH
 
	
 
Change from baseline in WPAI-GH item scores at Week 26
 

 
To compare LY900014 and insulin lispro with respect to changes in body weight
 
	
 
Change from baseline to Week 26 in weight (kg)
 

 
To compare LY900014 and insulin lispro with respect to glycemic variability
 
	
 
Within-day and between-day glycemic variability measured by the standard deviation and the coefficient of variation of 10-point SMBG profiles
 

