**Baseline and Post-Baseline Definitions and Patient Population by Study Period and Type of Analysis**

Study Period/Analysis	Patient Population	Baseline Observations	Post-Baseline Observations
1,5-AG	All Randomized Patients with a baseline and at least one post-baseline observation	Visit 8 prior to initiation of IP	Visits 11, 15, and 18 prior to discontinuation of IP AND Last of Visits 9-18 prior to discontinuation of IP

Health outcomes: ITSQ, EQ-5D-5L, EQ- VAS, WPAI-GH	All Randomized Patients with a baseline and a post- baseline observation	Last of Visits 1-8	Last of Visits 9-18 prior to discontinuation of IP
Safety Laboratory Tests (chemistry, hematology, lipids) – continuous analysis	All Patients in the Safety Population with a baseline and a post-baseline observation	Last of Visit 1-8	Visit 18 (planned) AND last of Visits 9-18 (planned including early discontinuation visits) regardless of IP use
Safety Laboratory Tests (chemistry, hematology, lipids) – categorical analysis	All Patients in the Safety Population with a normal baseline (with respect to the direction being analyzed) and a post- baseline observation	Visits 1-8 (including unplanned tests)	Visits 9-18 (including unplanned tests) regardless of IP use
TEAEs	All Patients in the Safety Population	Prior to first dose of randomized IP (or Visit 8 date if the dose date is missing) but after the first dose of open-label insulin lispro in the Lead-in Period	From first dose of randomized IP to last dose of randomized IP AND From first dose of randomized IP to Visit 801
Hypoglycemia events	Safety Population	All Visits 2-8	All Visits 9-18 prior to discontinuation of IP
Weight and vital signs	All Patients in the Safety Population with a baseline and a post-baseline observation	Last of Visits 2-8	Visits 9-18 prior to discontinuation of IP AND Visits 9-801 regardless of IP use
Anti-insulin lispro antibodies	Safety Population	Visit 2	Visits 3-801 regardless of IP use

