#### 6.12.7.1. Treatment Emergent Anti-Insulin Lispro Antibody

The treatment-emergent anti-insulin lispro antibody (denoted as treatment-emergent antidrug antibody [TEADA] throughout this SAP) is based on the change from baseline (Visit 2) to post-baseline (post-Visit 2) in the anti-insulin lispro antibody level (percent binding). Treatment-emergent antidrug antibody can be sub-classified as either treatment-induced (not detected anti-insulin lispro antibody at baseline) or treatment-boosted (detected anti-insulin antibody at baseline):

The TEADA status during the analysis period will be determined using all data in the corresponding analysis period regardless of IP use. The summary for TEADA status and the anti-insulin lispro antibody level will use the same analysis data.

The number and percentage of patients with positive TEADA response during the analysis period of Visit 2 to Visit 801 will be summarized by treatment group. For patients with positive TEADA response any time during the analysis period, the number and percentage of patients with positive insulin cross-reactivity anytime during the analysis period, and the number and percentage of patients not meeting the TEADA criteria at Visit 801 will also be summarized by treatment group. Treatment groups will be compared by Fisher's exact test.

Both actual and change from baseline (Visit 2) for the anti-insulin lispro antibody level in percent binding will be summarized by scheduled visit prespecified in the protocol for patients with positive TEADA response from Visit 2 to Visit 801. The repeated measurement from Visit 2 to Visit 801 will be analyzed by an MMRM model with treatment, baseline value of the response variable, visit, and visit by treatment interaction as fixed factors and patient as the random factor. The ANCOVA model using treatment and baseline value as covariates will be used for the analysis of last non-missing observation prior to or at Visit 801 and the analysis of maximum percent binding during the analysis period of Visit 2 to Visit 801. Plot of anti-insulin lispro antibody percent binding will be generated based on the MMRM and the ANCOVA models.

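### The only visible by-arm count of treatment-emergent antibodies starts at Visit 2, so responses from the open-label lispro lead-in enter the randomized comparison; add a count that starts at randomization

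*SAP*

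**What the plan says.** The exploratory objective in SAP Table 4.1 is a between-treatment comparison: "To compare the incidence of treatment-emergent anti-insulin lispro antibodies for LY900014 and insulin lispro".

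SAP 6.12.7 takes the antibody baseline before any study-provided prandial insulin: "Therefore, the blood sample result at Visit 2 will be considered as the anti-insulin lispro level at baseline for this study". The antibody row of SAP Table 6.2 defines the post-baseline observations as "Visits 3-801 regardless of IP use". SAP 6.12.7.1 then states that the number and percentage of patients with a "positive TEADA response during the analysis period of Visit 2 to Visit 801 will be summarized by treatment group", with Fisher's exact test between the arms. (TEADA is the SAP's term for treatment-emergent antidrug antibody.)

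Protocol 5.1 says that "all patients will be treated with insulin lispro throughout the lead-in period". The row "Anti-insulin lispro antibodies" in the Schedule of Activities (Protocol 2) has samples at Visit 2, at Visit 8 and at later visits. Footnote c of that schedule says: "Randomization should occur after all Visit 8 procedures including MMTT".

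**The concern.** The Visit 8 sample is drawn before randomization but is classed as post-baseline. A patient who converts during the lead-in is counted as treatment-emergent positive under an arm that had not yet been assigned. Randomized treatment cannot have caused that response, yet the objective is to compare the randomized treatments.

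The same Table 6.2 handles adverse events differently. There the lead-in is the baseline for the treatment period, and one of the two counting windows reads "From first dose of randomized IP to Visit 801"; both start at the first randomized dose. Lead-in adverse events are tabulated separately under open-label insulin lispro (SAP Table 6.4). Antibodies have neither a post-randomization count nor a separate lead-in summary in the visible text.

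At stake is the sensitivity of a safety comparison for a new formulation. Lead-in responses add the same expected background to both arms, which pulls the risk ratio towards 1 and could hide an excess on LY900014.

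**Working it through.** **Plan's own figure.** The documents state no antibody rate, power or sample size, so there is nothing on this endpoint to reproduce. The group sizes come from 564 randomized at 2:1 (SAP 5.2): 564 × 2/3 = 376 and 564 / 3 = 188. The two-sided alpha of 0.05 is from SAP 6.1.

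**Assumptions, not document figures.** Let q be the share of patients converting in the lead-in, equal in expectation between arms because of randomization. Let p be the post-randomization incidence in an arm.

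- Visit 2 baseline: counted incidence = q + (1 − q)p.
- Visit 8 baseline, if lead-in converters do not respond again: (1 − q)p.

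**One case in full** (p = 25% on LY900014, 15% on lispro, q = 5%):

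- Visit 2 baseline: 0.05 + 0.95 × 0.25 = 28.75%, and 0.05 + 0.95 × 0.15 = 19.25%. Risk ratio 28.75 / 19.25 = 1.49.
- Visit 8 baseline: 0.95 × 0.25 = 23.75%, and 0.95 × 0.15 = 14.25%. Risk ratio 1.67.
- Risk difference: 9.5 points under both baselines.
- Share of counted cases that predate randomization: 5 / 28.75 = 17% on LY900014 and 5 / 19.25 = 26% on lispro.

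**Power.** Two-sided Fisher's exact test at 0.05, by full enumeration of both binomials (376 and 188, no simulation). Entries are Visit 2 baseline / Visit 8 baseline.

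| Assumed p, LY900014 vs lispro | q = 2% | q = 5% | q = 10% | q = 20% |
|---|---|---|---|---|
| (a) 25% vs 15% | 74 / 77% | 68 / 76% | 59 / 73% | 44 / 66% |
| (b) 15% vs 7% | 72 / 79% | 62 / 77% | 50 / 75% | 33 / 69% |
| (c) 45% vs 33% | 77 / 77% | 74 / 74% | 68 / 70% | 56 / 62% |

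In case (a) the Visit 2 risk ratio is 1.59, 1.49, 1.38 and 1.25 across the four values of q, against 1.67 from Visit 8. The risk difference is 9.8, 9.5, 9.0 and 8.0 points under either baseline. If lead-in converters could respond again at rate p, Visit 8 power in case (a) would be 78% at every q.

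**Type I error.** With 15% in both arms and q = 0, 10% and 20%, the exact rate is 4.3%, 4.4% and 4.5% from Visit 2, and 4.3% each from Visit 8.

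**Do other outputs fill the gap?** SAP 6.12.7.1 also plans a by-visit listing, percent-binding summaries by visit, and repeated-measures and covariance models of binding. The listing makes no between-arm comparison. The by-visit summaries are confined to TEADA-positive patients, and the models concern binding level, not incidence. The cross-reactivity count and the count no longer meeting the criteria at Visit 801 are taken within the same Visit 2 to Visit 801 positives.

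**The case against.** The strongest reply is that Visit 2 is a deliberate and coherent choice. The antibody measured is to insulin lispro, lispro is given in the lead-in and in both arms, and the sample precedes study-provided lispro. Protocol 10.3.1 allows a baseline other than Visit 8 where one is specified, and Protocol 10.3.4 leaves immunogenicity analysis to the SAP. The SAP also shows lead-in insulin doses and weight by the arm assigned later, so the adverse-event row is not its only convention. All of this stands, and it is why the Visit 2 summary should be kept. It does not supply the comparison that the objective names.

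Second, the analysis might exist in text that cannot be seen. The SAP revision history mentions a randomization-to-Week 26 period for some safety analyses, the list of analysis periods in SAP 6.1 has an empty bullet, and a sentence in 6.12.7.1 ends in a colon with no criteria after it. This also stands as a caveat: the only period that the visible text names for TEADA is Visit 2 to Visit 801.

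Third, the size is assumed throughout. Patients have had at least 90 days of insulin before screening, and prior lispro is allowed, so lead-in conversion may be rare. In case (c) the loss is under one point at q = 2% and 5%, and two points at 10%. The risk difference does not change at all if converters do not respond again. The power figures are illustrations, not an expected loss.

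Finally, a Visit 8 baseline can classify a patient who still carries lead-in antibodies as negative, and the TEADA threshold is not visible. That is a reason to report both counts and to leave the subgroup definition alone.

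**Conclusion.** The point holds as a low-priority improvement. By the plan's own definitions, responses that predate randomization enter the by-arm Fisher comparison, and no visible output gives a by-arm incidence starting at randomization.

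The consequence is dilution of the risk ratio and loss of power, not bias towards an arm and not type I error inflation. Across the assumed scenarios the power loss runs from almost nothing (case (c), q = 2%) to 36 points (case (b), q = 20%: 33% against 69%). Which end applies depends on the lead-in conversion rate, which the documents do not give. These figures assume equal expected lead-in conversion in the two arms, no second response in lead-in converters, and all 564 patients contributing. The primary and multiplicity-adjusted conclusions are unaffected.

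**What to change.** In SAP 6.12.7.1, add one by-arm TEADA incidence comparison that uses the Visit 8 sample as baseline (Visit 2 if Visit 8 is missing) and only post-randomization samples through Visit 801, with Fisher's exact test as already planned. Report TEADA arising between Visit 2 and Visit 8 separately, as a pooled open-label insulin lispro summary. Keep the Visit 2-based table and label it as the cumulative response to study lispro. Leave the TEADA-status subgroup definition unchanged.

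The cost is one sentence in 6.12.7.1, one row in Table 6.2, one derived flag and one table. No new samples are needed. The drawback is that the report will carry two TEADA figures, and the difference between them must be explained. If such an analysis already exists in text not visible here, confirming that is enough.

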#### 6.12.7.1. Treatment Emergent Anti-Insulin Lispro Antibody

The treatment-emergent anti-insulin lispro antibody (denoted as treatment-emergent antidrug antibody [TEADA] throughout this SAP) is based on the change from baseline (Visit 2) to post-baseline (post-Visit 2) in the anti-insulin lispro antibody level (percent binding). Treatment-emergent antidrug antibody can be sub-classified as either treatment-induced (not detected anti-insulin lispro antibody at baseline) or treatment-boosted (detected anti-insulin antibody at baseline):

The TEADA status during the analysis period will be determined using all data in the corresponding analysis period regardless of IP use. The summary for TEADA status and the anti-insulin lispro antibody level will use the same analysis data.

The number and percentage of patients with positive TEADA response during the analysis period of Visit 2 to Visit 801 will be summarized by treatment group. For patients with positive TEADA response any time during the analysis period, the number and percentage of patients with positive insulin cross-reactivity anytime during the analysis period, and the number and percentage of patients not meeting the TEADA criteria at Visit 801 will also be summarized by treatment group. Treatment groups will be compared by Fisher's exact test.

Both actual and change from baseline (Visit 2) for the anti-insulin lispro antibody level in percent binding will be summarized by scheduled visit prespecified in the protocol for patients with positive TEADA response from Visit 2 to Visit 801. The repeated measurement from Visit 2 to Visit 801 will be analyzed by an MMRM model with treatment, baseline value of the response variable, visit, and visit by treatment interaction as fixed factors and patient as the random factor. The ANCOVA model using treatment and baseline value as covariates will be used for the analysis of last non-missing observation prior to or at Visit 801 and the analysis of maximum percent binding during the analysis period of Visit 2 to Visit 801. Plot of anti-insulin lispro antibody percent binding will be generated based on the MMRM and the ANCOVA models.

A listing of anti-insulin lispro antibody at each visit will be provided. The listing will include anti-insulin lispro antibody status (detected/not detected), anti-insulin lispro antibody percent binding, TEADA status (positive/negative), insulin cross-reactivity status, and insulin cross-reactivity percent binding for the safety population.

Subgroup analysis for the following selected efficacy and safety variables will be performed by the TEADA status during the analysis period of Visit 2 to Visit 801:

- Use data prior to discontinuation of IP:
  - HbA1c and change from baseline in HbA1c
  - 1-hour and 2-hour PPG excursions
  - basal, prandial, and total insulin dose
  - event rate of overall hypoglycemic events
- Use all data regardless of IP use:
  - treatment-emergent injection site reaction and hypersensitivity reaction

The analyses for HbA1c and change from baseline in HbA1c will be performed using an MMRM model for the primary analysis and the HbA1c data prior to permanent discontinuation of IP. Besides treatment, the model will include additional fixed terms of subgroup, subgroup by treatment interaction, subgroup by visit interaction, and 3-way interaction of treatment, subgroup and visit.

The PPG excursions will be analyzed by the ANCOVA model same as the model specified in Section 6.11.2 with data collected before permanent discontinuation of IP. The model will include additional terms of subgroup, subgroup by treatment interaction, subgroup by visit interaction, and 3-way interaction of treatment, subgroup and visit.

The subgroup analysis for insulin dose will use the MMRM model specified in Section 6.11.5 using data collected before permanent discontinuation of IP. The model will include additional

fixed terms of subgroup, subgroup by treatment interaction, subgroup by visit interaction, and 3-way interaction of treatment, subgroup and visit.

The treatment-emergent injection site reaction and hypersensitivity reaction will be analyzed by a logistic regression model including terms of treatment, subgroup, treatment by subgroup interaction. All data regardless of IP use will be used for this analysis.

The negative binomial regression model specified in [Table 6.5](#) with additional terms of subgroup, treatment by subgroup interaction will be used for the subgroup analysis of overall hypoglycemia event rate while on IP.

The interaction effects (3-way for MMRM and 2-way for ANCOVA/logistic regression model/negative binomial regression model) will be evaluated using a significance level of 0.10, unadjusted. If the interaction effect is significant ( $p < 0.10$ ), separate analysis without the terms related with the subgroup will be performed for each subpopulation.

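### Insulin cross-reactivity and antibody persistence are tested between arms only among patients who became TEADA-positive, and the population for the antibody-level models is left unclear

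*SAP*

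**What the plan says.** SAP 6.12.7.1 builds the selection variable from the antibody measurement itself. TEADA "is based on the change from baseline (Visit 2) to post-baseline (post-Visit 2) in the anti-insulin lispro antibody level (percent binding"). The analyses then use different sets of patients:

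- **Incidence.** "The number and percentage of patients with positive TEADA response during the analysis period of Visit 2 to Visit 801 will be summarized by treatment". This is not conditioned on TEADA.
- **Cross-reactivity.** "For patients with positive TEADA response any time during the analysis period, the number and percentage of patients with positive insulin cross-reactivity" is reported, so positives are the denominator.
- **Persistence.** In the same sentence, and so with the same denominator, "the number and percentage of patients not meeting the TEADA criteria at Visit 801 will also be summarized by treatment group".
- **Test.** The paragraph closes with "Treatment groups will be compared by" Fisher's exact test, which reads as covering all three.
- **Level, summaries.** Actual and change values of percent binding "will be summarized by scheduled visit prespecified in the protocol for patients with positive TEADA response from Visit 2 to Visit 801".
- **Level, models.** "The repeated measurement from Visit 2 to Visit 801 will be analyzed by an MMRM model with treatment" and further terms. ANCOVAs for the last and the maximum value follow. None of these sentences names a population.

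Elsewhere, SAP 6.1 makes the Safety Population the default for safety analyses. SAP 6.12 sends the reader to Tables 6.1 and 6.2 for populations, and the antibody row of Table 6.2 gives the Safety Population with Visit 2 as baseline. Beyond the incidence comparison, 6.12.7.1 provides a Safety-population listing of level, TEADA status and cross-reactivity.

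**The concern.** Randomization makes the arms comparable as a whole. It does not make the TEADA-positive patients in one arm comparable with those in the other, because most of the time over which positivity is decided lies after randomization. If LY900014 turned additional, weaker responders positive, they would enlarge its denominator and pull down its average among positives. The percentage cross-reactive could then look equal or lower on the more immunogenic product, and differences in persistence and level could be muted. These are the planned between-arm analyses of the character of the antibody response, which incidence does not measure.

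**Working it through.** **Inputs.** The SAP gives no power figure, positivity rate, cut-off or distribution for antibodies. The arm sizes follow from its sample size section: 564 randomized at 2:1 is 376 on LY900014 and 188 on lispro. Every antibody figure below is an assumption.

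**Cross-reactivity.** Let r be the proportion of all patients who are positive and cross-reactive, and π the proportion positive. The SAP compares r/π between arms. The direction reverses whenever LY900014 has the higher r but the ratio of the r values is smaller than the ratio of the π values. Fisher p-values are two-sided, and LY900014 is given first.

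| Assumed TEADA-positive | Cross-reactive, all patients | Cross-reactive, positives only |
|---|---|---|
| 30% vs 20% (113 vs 38) | 45/376 = 12.0% vs 19/188 = 10.1%, p = 0.57 | 45/113 = 39.8% vs 19/38 = 50.0%, p = 0.34 |
| 40% vs 25% (150 vs 47) | 75/376 = 19.9% vs 28/188 = 14.9%, p = 0.17 | 75/150 = 50.0% vs 28/47 = 59.6%, p = 0.32 |
| 45% vs 25% (169 vs 47) | 75/376 = 19.9% vs 28/188 = 14.9%, p = 0.17 | 75/169 = 44.4% vs 28/47 = 59.6%, p = 0.07 |
| 30% vs 30% (113 vs 56), no effect | 56/376 = 14.9% vs 28/188 = 14.9%, p = 1.00 | 56/113 = 49.6% vs 28/56 = 50.0%, p = 1.00 |

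In the second row, 19.9/14.9 = 1.34 and 39.9/25.0 = 1.60, so the ratio among positives is 1.34/1.60 = 0.84. The counts were chosen to show the mechanism and predict nothing.

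**Persistence.** A simulation used 400 trials per setting, with six samples after Visit 2, the first before randomization. A patient was positive if the highest value reached a cut-off, and the last sample stood in for Visit 801. With a uniform shift of 0.5 between-patient SD on LY900014 and a cut-off of 1.0 SD:

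- still above the cut-off at the last sample, all patients: 32.8% vs 18.4%, a gap of 14.4 points;
- no longer above it, positives only: 39.7% vs 44.9%, a gap of 5.2 points.

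At cut-offs of 1.5 and 2.0 SD the gaps are 9.5 against 3.2 points and 5.4 against 3.0 points. Persistence shrank here but did not reverse.

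**Level, if restricted to positives.** For one normal measurement with 20% of lispro patients positive, the cut-off is c = 0.842. With a shift of δ = 0.3 SD:

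- LY900014 positive: 1 − Φ(0.842 − 0.3) = 29.4%;
- mean of lispro positives: φ(0.842)/0.200 = 1.400;
- mean of LY900014 positives: 0.3 + φ(0.542)/0.294 = 1.472;
- difference: 0.072 SD, so 1 − 0.072/0.3 = 76% of the true difference is lost.

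Over shifts of 0.2 to 0.5 SD and 10% to 40% positive, the loss is 64% to 82%. The repeated-sample simulation agrees: for shifts of 0.25 to 1.0 SD, 15% to 34% of the difference in the last value remained.

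Reversal needed a particular pattern. With 15% strong responders in both arms and 10% to 30% of the other LY900014 patients lifted just over the cut-off, all-patient differences of +0.10 to +0.31 became −0.23 to −1.07 among positives. Lifting the same fractions within a single normal distribution only shrank the difference, from 0.13–0.50 to 0.05–0.15. With no treatment effect, both differences were within 0.02 of zero.

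**Timing.** In the uniform-shift simulations, 1% to 23% of positives had already crossed the cut-off before randomization. Positivity is therefore largely, but not wholly, a post-randomization event.

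**The case against.** A reader might infer that the level models are confined to TEADA-positive patients. The text does not establish that. The restriction sits in the sentence on summaries, the model sentences are silent, and SAP 6.1, 6.12 and Table 6.2 point to the Safety Population. On that reading the models already use nearly the right set. This objection stands for the MMRM and ANCOVAs, where the defect is ambiguity. It does not reach cross-reactivity and persistence, where the TEADA-positive denominator is explicit.

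A reader might also infer that no randomized comparison of immunogenicity is planned. That is wrong. TEADA incidence is tested without this conditioning and is the only immunogenicity endpoint in the objectives. In the 0.3 SD example it would show 29.4% vs 20%, so an excess would be visible. All-patient cross-reactivity percentages could also be worked out from the reported counts.

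The stakes are limited. The objective is exploratory, outside the multiplicity scheme, and no decision rule depends on it. Asking how many positives cross-react, or have resolved, is a fair descriptive question. What does not stand is attaching a between-arm test to the answer as though it were a randomized comparison.

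**Conclusion.** The point holds for the tested contrasts in cross-reactivity and persistence. They condition on a largely post-randomization status derived from percent binding, and they can understate or invert a true arm difference. The by-visit percent-binding summaries share the restriction. For the MMRM and both ANCOVAs the SAP can be read either way and should be made definite.

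The weight is minor to moderate. The documents do not support a stated size of distortion: every rate, shift and cut-off above is assumed. The single-measurement model is simpler than TEADA, which uses change over several visits, and the planned level models adjust for baseline. Nor do the examples show a false significant result, since no Fisher test above falls below 0.05. Shrinkage occurred in every setting with a uniform true shift. Reversal depends on the response pattern or, for cross-reactivity, on the chosen rates. The distortion arises only if the products differ, which is the situation these analyses are meant to describe.

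**What to change.** Amend SAP 6.12.7.1 as follows.

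- Test cross-reactivity (TEADA-positive and cross-reactive) and TEADA still present at Visit 801 with all Safety-population patients in each arm as denominator. Say how a missing Visit 801 sample is counted.
- State that the percent-binding MMRM and both ANCOVAs use all Safety-population patients with a Visit 2 value and a later value.
- Keep the TEADA-positive tables as descriptive, without between-arm p-values.

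The cost is SAP wording and a few more table columns. No new data are needed: sampling covers all enrolled patients from Visit 2, and the Safety-population listing already holds level, TEADA status and cross-reactivity. The all-patient percentages will be smaller and say less about the character of the response among positives, which the retained descriptive tables cover.
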